## 4.2 Informed Consent

For patients not previously participating in a study investigating Lu AF35700, written informed consent must be obtained before the Screening Visit in this study. For patients previously participating in a study investigating Lu AF35700, written informed consent must be obtained before the Baseline Visit in this study.

No study-related procedures, including any screening procedures, may be performed before the investigator has obtained written informed consent from the patient and/or his or her legal representative (if applicable).

Changing (for example, discontinuing or down-tapering) a patient's concomitant medications prior to the Screening Visit to ensure that the patient meets the selection criteria is a study-related activity and must not occur before the *Informed Consent Form* has been signed.

As fasting samples are to be taken at the Screening Visit, the *Informed Consent Form* must be signed a suitable number of days before the Screening Visit.

If the informed consent process may be delegated, the requirements for the delegates must be documented prior to the start of the study. National laws must always be adhered to when allowing potential delegation. Any delegation must be documented in the site delegation log.

The Investigator must exclude any adult patient who lacks capacity to consent for himself/herself from participation in the study. The investigator must identify vulnerable patients, that is, patients whose willingness to participate in this study might be unduly influenced by the expectation, regardless of whether it is justified, of benefits associated with participation, or of a retaliatory response from senior members of a hierarchy in case of refusal to participate. Patients thus identified must be excluded from participation in the study.

Prior to obtaining written informed consent, the investigator or a designee must explain to the patients and their legal representatives (if applicable) the aims, methods, and potential hazards of the study and any discomfort it may entail. The patients and their legal representatives (if applicable) must be informed that their participation in the study is voluntary and that they are free to withdraw from the study at any time without justifying their decision. The patients and their legal representatives (if applicable) must be informed of the possibility of withdrawing consent (section 8.4).

The patients and their legal representatives (if applicable) must be given ample time and opportunity to enquire about details of the study prior to deciding whether to participate in the study.

The *Informed Consent Form* includes a statement whereby the patient agrees to communicate with their regular doctor of their participation in the study. If the patient does not want his/her regular doctor to be contacted and there is no other way to verify or establish that the patient qualifies for the study, the patient should not be enrolled.

It is the responsibility of the investigator to ensure that all questions about the study are answered to the satisfaction of the patients and their legal representatives (if applicable). Prior to including a patient in the study, an *Informed Consent Form* must be signed and dated by the patient and his or her legal representative (if applicable) and signed and dated by the investigator or a designee. The patients and their legal representatives (if applicable) must receive a copy of the written information (*Patient Information Sheet*) as well as a copy of the signed *Informed Consent Form*.

The consent procedures described above will only be implemented if allowed by local law and regulations and will only be initiated after approval by the relevant ethics committees (IECs) or institutional review boards (IRBs).

The blood samples for exploratory biomarker analysis may be shared with academic or public institutions; however, Lundbeck will remain full control of the samples and their use on accordance with the information in the *Patient Information Sheet* and a material transfer agreement.

### **4.3 Personal Data Protection**

In accordance with European Union Directive 95/46/EC, the data will be processed in accordance with the specifications outlined by the Danish Data Protection Agency to ensure that requirements regarding personal data protection are met. If an external organisation will process data on behalf of Lundbeck, a contractual procedure will be signed between Lundbeck and the external organisation to ensure compliance with the above-mentioned legislation.

If applicable, the participation of patients in this study will be reported to the appropriate local data protection agencies, in accordance with European Union Directive 95/46/EC and country-specific guidelines and laws.

### **4.4 Independent Ethics Committee(s) (IEC(s)) and Institutional Review Board(s) (IRB(s))**

This study will be conducted only after approval of the protocol has been granted by the appropriate IEC or IRB and a copy of the written approval has been received by Lundbeck.

The investigator must not screen or include any patients before receiving written approval from the IEC or IRB.

The IEC or IRB must be informed when specific types of protocol amendments have been made and must be asked whether a re-evaluation of the ethical aspects of the study is necessary.

If applicable, interim reports on the study and reviews of its progress will be submitted to the IEC or IRB by the investigator at intervals stipulated in its guidelines.

#### **4.5 Regulatory Approval/Notification Requirements**

In accordance with local requirements, this study will be submitted to the regulatory authorities for approval or notification. The study will only be undertaken when Lundbeck has received written approval or confirmation of notification from the regulatory authorities.

## **5 Study Population**

### **5.1 Numbers of Patients and Sites**

Planned regions:

North America, Europe and South America

Approximately planned number of patients:

to be enrolled:	400
to complete the study:	200

Approximately planned number of:

study sites:	120
--------------	-----

### **5.2 Recruitment of patients who can potentially benefit from treatment with Lu AF35700**

The recruitment of patients who can potentially benefit from treatment with Lu AF35700 can start in a given site only after the recruitment of the patients in the study 16159A or in the study 16323A is completed.

Competitive patient recruitment between countries and sites will be used during the entire recruitment period to ensure that the required number of patients is enrolled within the planned recruitment period.

The investigators will be notified immediately when the recruitment period comes to an end.

### 5.3 Selection Criteria

Patient selection to study 16159B is based on the inclusion and exclusion criteria listed below.

Patients who meet each of the inclusion criteria at the Screening Visit (unless otherwise specified) and none of the exclusion criteria at the Screening Visit (unless otherwise specified) are eligible to participate in this study.

#### Inclusion Criteria

##### For patients who completed study 16159A

Patients who meet each of the inclusion criteria and none of the exclusion criteria at the Baseline Visit (unless otherwise specified; some criteria assessed as part of the Primary Outcome Visit in study 16159A) are eligible to participate in this study.

1. The patient has completed study 16159A.
2. The patient is still capable of communicating with the site personnel.
3. The patient and if applicable his or her legal representative is/are able to read and understand the *Informed Consent Form*.
4. The patient and if applicable his or her legal representative has/have signed the *Informed Consent Form* for study 16159B.
5. The patient is willing and able to attend study appointments within the specified time windows.
6. The patient can potentially benefit from 52-week treatment with Lu AF35700 according to the investigator's clinical judgment.
7. The patient has a caregiver or an identified responsible person considered reliable by the investigator (for example, family member, social worker, case worker, or nurse) considered reliable by the investigator in providing support to the patient to ensure compliance with study treatment, outpatient visits, and protocol procedures.
8. The patient has a stable living environment, as demonstrated by the ability to provide contact information for themselves and/or family/friend(s)/caregiver(s).
9. The patient, if a woman, must:
  - agree not to try to become pregnant during the study, AND
  - use adequate, highly effective contraception (defined as those that result in a low failure rate [that is, <1% per year] when used consistently and correctly, for example, implants, injectables, combined oral contraceptives in combination with a double barrier method, some intrauterine devices, sexual abstinence, vasectomised partner), OR
  - have had her last natural menstruation  $\geq 28$  months prior to the Primary Outcome Visit in study 16159A, OR
  - have been surgically sterilised prior to the Primary Outcome Visit in study 16159A, OR
  - have had a hysterectomy prior to the Primary Outcome Visit in study 16159A.
10. The patient, if a man, must:
  - use two methods of contraception in combination if his female partner is of childbearing potential; this combination of contraceptive methods must be used from the Baseline Visit to  $\geq 3$  months after the last dose of IMP, OR

- have been surgically sterilised prior to the Primary Outcome Visit in study 16159A.

The following assessments from the Primary Outcome Visit in study 16159A will be linked to the Baseline Visit: PANSS, CGI-S, PSP, NSA-4, QLS, TooL, MSQ, WorQ, HEA, ongoing adverse events, physical examination, waist circumference, weight, vital signs, 12-lead ECG, mSAS, AIMS, BARS, C-SSRS, ongoing concomitant medication, clinical safety laboratory data (including S-βhCG pregnancy test, HBA1c, blood lipid profile) (see [Panel 2](#)).

Additionally, diagnosis, demographics, relevant medical, psychiatric and social history and height will be linked from the Screening Visit in study 16159A to Baseline Visit in this study.

*For patients who completed the dosing period of study 16323A*

Patients who meet each of the inclusion criteria and none of the exclusion criteria at the Baseline Visit (unless otherwise specified; some criteria assessed as part of the last visit of the dosing period in study 16323A) are eligible to participate in this study.

1. The patient has completed the dosing period of study 16323A.
2. The patient is still capable of communicating with the site personnel.
3. The patient and if applicable his or her legal representative is/are able to read and understand the *Informed Consent Form*.
4. The patient and if applicable his or her legal representative has/have signed the *Informed Consent Form* for study 16159B.
5. The patient is willing and able to attend study appointments within the specified time windows.
6. The patient can potentially benefit from 52-week treatment with Lu AF35700 according to the investigator's clinical judgment.
7. The patient has a caregiver or an identified responsible person considered reliable by the investigator (for example, family member, social worker, case worker, or nurse) considered reliable by the investigator in providing support to the patient to ensure compliance with study treatment, outpatient visits, and protocol procedures.
8. The patient has a stable living environment, as demonstrated by the ability to provide contact information for themselves and/or family/friend(s)/caregiver(s).
9. The patient, if a woman, must:
  - agree not to try to become pregnant during the study, AND
  - use adequate, highly effective contraception (defined as those that result in a low failure rate [that is, <1% per year] when used consistently and correctly, for example, implants, injectables, combined oral contraceptives in combination with a double barrier method, some intrauterine devices, sexual abstinence, vasectomised partner), OR
  - have had her last natural menstruation  $\geq 28$  months prior to the Primary Outcome Visit in study 16323A, OR
  - have been surgically sterilised prior to the last visit of the dosing period in study 16323A, OR
  - have had a hysterectomy prior to the last visit of the dosing period in study 16323A.

10. The patient, if a man, must:
  - use two methods of contraception in combination if his female partner is of childbearing potential; this combination of contraceptive methods must be used from the Baseline Visit to  $\geq 3$  months after the last dose of IMP, OR
  - have been surgically sterilised prior to the last visit of the dosing period in study 16323A.
11. The patient has a confirmed diagnosis of schizophrenia according to DSM-5TM.
12. The patient is willing to discontinue all prohibited psychotropic medications to meet protocol-required washout prior and during the study.

*For patients who can potentially benefit from treatment with Lu AF35700*

Patients who meet each of the inclusion criteria at the Screening and Baseline Visits (unless otherwise specified) and none of the exclusion criteria at the Screening and Baseline Visits (unless otherwise specified) are eligible to participate in this study.

1. The patient is capable of communicating with the site personnel.
2. The patient and if applicable his or her legal representative is/are able to read and understand the *Informed Consent Form*.
3. The patient and if applicable his or her legal representative has/have signed the *Informed Consent Form* for study 16159B.
4. The patient is willing and able to attend study appointments within the specified time windows.
5. The patient is either an inpatient at a psychiatric setting or outpatient consulting a psychiatrist.
6. The patient has schizophrenia, diagnosed according to DSM-5TM.
7. The patient is a man or woman, aged  $\geq 18$  years.
8. The patient has been prescribed an oral antipsychotic treatment at recommended dose range as stated in the SmPC or equivalent document/label for 6 weeks prior the Screening Visit.
9. The patient has a PANSS total score of  $\geq 60$  and  $\leq 90$  at Screening and Baseline Visits.
10. The patient has a Clinical Global Impression-Severity of Illness (CGI-S) score  $\leq 4$
11. The patient is in need of a change in the current antipsychotic treatment and according to the investigator's clinical, the patient would potentially benefit from a switch to another treatment, including but not limited to any of the following reasons:
  - lack of adequate response to his or her current antipsychotic medication,
  - poor tolerability to his or her current antipsychotic medication,
  - unwillingness of the patient to adhere to his or her current antipsychotic medication.
13. The patient is willing to discontinue all prohibited psychotropic medications to meet protocol-required washout prior and during the study.
14. The patient has a caregiver or an identified responsible person (for example, family member, social worker, case worker, or nurse), considered reliable by the investigator in providing support to the patient to ensure compliance with study treatment, outpatient visits, and protocol procedures.

15. The patient has a stable living environment, as demonstrated by the ability to provide contact information for themselves and/or family/friend(s)/caregiver(s).
16. The patient, if a woman, must:
  - agree not to try to become pregnant during the study, AND
  - use adequate, highly effective contraception (defined as those that result in a low failure rate [that is, <1% per year] when used consistently and correctly, for example, implants, injectables, combined oral contraceptives in combination with a double barrier method, some intrauterine devices, sexual abstinence, vasectomised partner), OR
  - have had her last natural menstruation  $\geq 12$  months prior to the Screening Visit, OR
  - have been surgically sterilised prior to the Screening Visit, OR
  - have had a hysterectomy prior to the Screening Visit
17. The patient, if a man, must:
  - use 2 methods of contraception in combination if his female partner is of childbearing potential; this combination of contraceptive methods must be used from the Baseline Visit to  $\geq 1$  month after the last dose of IMP, OR
  - have been surgically sterilised prior to the Screening Visit

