### 1.1.2 Nonclinical Pharmacology Data

Lu AF35700 is a novel deuterated compound with affinity for serotonergic, dopaminergic, and  $\alpha$ -adrenergic receptors, and acts as an antagonist of those receptor types. The multi-receptor profile of Lu AF35700 is believed to have an antipsychotic effect.

Lu AF35700 has similar high affinity for the human serotonergic 5-HT2A and 5-HT6 receptors. Like “atypical antipsychotics”, the affinity for the human 5-HT2A receptor is substantially

higher than for the dopamine D2 receptor. Distinctively, Lu AF35700 has higher affinity for the human dopamine D1 receptor than it has for the human dopamine D2 receptor.

The *in vitro* receptor profile of high affinity for 5-HT2A and 5-HT6 receptors and low affinity for dopamine D2 receptors was confirmed by *in vivo* occupancy studies. The predicted steady-state concentration resulting in 50% target occupancy (EC50) was calculated based on *in vivo* occupancy and pharmacokinetic (PK) data from rats. The EC50 for 5-HT6 (12 ng/mL) and 5-HT2A (20 ng/mL) receptors is equipotent and much lower than for dopamine D1 (115 ng/mL) and dopamine D2 (255 ng/mL) receptors.

The potent binding to dopamine D1 receptors combined with a lower affinity for the dopamine D2 receptors is believed to result in a beneficial efficacy profile and a tolerability profile without the troublesome adverse effects associated with extensive dopamine D2 receptor blockade, such as extrapyramidal symptoms (EPS), hyperprolactinaemia, sexual dysfunction, and dysphoria/anhedonia. Furthermore, given the lack of muscarinic receptor blockade, it is expected that Lu AF35700 will not have a negative impact on cognitive performance related to muscarinic receptor inhibition.

In animal models, Lu AF35700 inhibited conditioned avoidance responding (CAR), amphetamine-induced hyperactivity, and phencyclidine (PCP)-induced hyperactivity at doses having no sedative or motor inhibiting effects, indicative of antipsychotic potential combined with few side effects.

[figure not shown]
Lu AF36152 is the major metabolite of Lu AF35700 and has a pharmacological *in vitro* and *in vivo* profile which is similar to that of Lu AF35700 although it is less potent *in vivo*.

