### 1.1.5.2 Pharmacokinetics

A preliminary integrated popPK analysis was performed on data from studies 14198A, 14754A, 15867A, and 15868A.

In the popPK model, the absorption phase was adequately described by first-order absorption (absorption rate constant  $[k_a] = 0.27$  L/h) with lag-time (1 h). The distribution profiles of both Lu AF35700 and Lu AF36152 were best described by two-compartment models with central and peripheral compartments. The population volume of distribution of Lu AF35700 and Lu AF36152 was estimated to 5442 and 4933 L, respectively. Plasma protein binding was investigated *in vitro* in human plasma and, overall, Lu AF35700 was classified as “highly” protein bound (95% to 99%). The apparent oral clearance of Lu AF35700 and Lu AF36152 was estimated to 29 L/h and 15 L/h, respectively. From the population estimates, the elimination half-life for Lu AF35700 and Lu AF36152 was estimated to 143 hours and 250 hours, respectively.

Preliminary results from the MAD study indicate that for the patients receiving therapeutically relevant doses of Lu AF35700, the parent compound at Day 21/24 had a median  $t_{max}$  of 8 hours, mean  $C_{max}$  ranging from 24.6 to 43.8 ng/mL, and mean area under the curve from zero to 24 hours ( $AUC_{0-24h}$ ) ranging from 455 to 759 ng·h/mL. For the major metabolite Lu AF36152, the corresponding values were a median  $t_{max}$  ranging from 9 to 14 hours, mean  $C_{max}$  ranging from 25.2 to 43.8 ng/mL, and mean  $AUC_{0-24h}$  ranging from 475 to 685 ng·h/mL.

Please refer to the *Investigator’s Brochure* for a summary of PK parameters.

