### **8.5 Safety Follow-up Visit/Contact (Visit 18)**

The safety follow-up is conducted to capture serious adverse events (SAEs) that occur during the Safety Follow-up Period as well as to follow up on the outcome of adverse events ongoing at the end of the Treatment Period. The safety follow-up must be conducted 42 days (+3 days) after the last dose of IMP. The safety follow-up may either be conducted as a visit to the site or as a telephone contact.

If any new SAEs have occurred since the last assessment at which the patient received IMP, the safety follow-up must, when possible, be a visit to the site.

For adverse events that were ongoing at the end of the Treatment Period and that resolved during the Safety Follow-up Period, the stop date must be recorded. For non-serious adverse events still ongoing at the safety follow-up, the stop date must be recorded as "ongoing". SAEs must be followed until resolution or the outcome is known.

Patients with a clinical safety laboratory test value that was out-of-range at the Primary Outcome or Withdrawal Visit and judged clinically significant must be followed according to accepted medical standards for up to 42 days or until the value normalises or stabilises or a diagnosis or a reasonable explanation has been established. For these patients, safety follow-up visits must be scheduled to allow for a medical examination and/or blood sampling. The investigator must decide whether further safety follow-up visits are required after 42 days. If further safety follow-up visits are made, these must be documented in the patient's medical record and not in the eCRF.

Patients who withdrew due to elevated AST or ALT values (see section 5.4) should be followed until the values normalise or stabilise or a diagnosis or a reasonable explanation has been established (see section 10.5).

The safety follow-up for patients who withdraw consent must be performed, if at all possible; any information collected will be recorded in the patients' medical records.

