## **8.6 End-of-study Definition**

The end of the study for an individual patient is defined as the last protocol-specified contact with that patient. The overall end of the study is defined as the last protocol-specified contact with the last patient ongoing in the study.

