#### **10.5 Treatment and Follow-up of Adverse Events**

Patients with adverse events must be treated in accordance with usual clinical practice at the discretion of the investigator.

Non-serious adverse events must be followed up until resolution or the safety follow-up assessment, whichever comes first. At the safety follow-up, information on new SAEs, if any, and stop dates for previously reported adverse events must be recorded.

It is the responsibility of the investigator to follow up on all SAEs until the patient has recovered, stabilised, or recovered with sequelae, and to report to Lundbeck all relevant new information using the same procedures and timelines as those for the initial report. Relevant information includes discharge summaries, autopsy reports, and medical consultations.

SAEs that are spontaneously reported by a patient to the investigator after the safety follow-up assessment must be handled in the same manner as SAEs that occur during the study. These SAEs will be captured in the PV database.

Patients with clinically significant out-of-range clinical safety laboratory test values at the Primary Outcome or Withdrawal Visit must be followed in accordance with usual clinical practice and be scheduled for a Safety Follow-up Visit to allow for a medical examination and/or blood sampling (see section 8.5).

Patients who withdraw due to elevated AST or ALT values (see section 5.4) must be followed until the values normalise or stabilise or a diagnosis or a reasonable explanation has been established. Additional medical examinations (for example, ultrasound scanning and/or sampling for serology, conjugated bilirubin, INR) should be considered. A gastroenterology or hepatology consultation should also be considered.

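### Roll-over women are bound only during the study (about 42 days after last dose) and roll-over men for at least 3 months, with no reason given

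*Protocol*

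**What the plan says.** Protocol 5.3 has one inclusion list for completers of study 16159A and one for completers of the dosing period of study 16323A. The relevant wording is the same in both.

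- **Women (criterion 9).** A woman must "agree not to try to become pregnant during the study, AND" and must "use adequate, highly effective contraception (defined as those that result in a low failure rate" (the text goes on to define the rate and give examples). Alternatives cover women past menopause, sterilised or after hysterectomy. The first bullet runs for the study. The second states neither a start nor a stop.
- **Men (criterion 10).** For a man whose partner is of childbearing potential, two methods are required, and "this combination of contraceptive methods must be used from the Baseline Visit to" at least 3 months after the last dose.

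Other sections fix what the study period means:

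- Section 8.6: "The end of the study for an individual patient is defined as the last protocol-specified contact with that patient".
- Section 8.5: "The safety follow-up must be conducted 42 days (+3 days) after the last dose of IMP".
- Section 3.1 lists a 6-week safety follow-up as one of the study periods, and the Synopsis counts roll-over participation through to the end of follow-up, up to 58 weeks.

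On clearance, section 1.1.5.2 reports that "the elimination half-life for Lu AF35700 and Lu AF36152 was estimated to 143 hours and 250 hours, respectively", from a population analysis it describes as preliminary. Section 1.1.2 says the metabolite has a pharmacological profile "which is similar to that of Lu AF35700 although it is less potent" in vivo.

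**The concern.** Women take the drug themselves and would carry any pregnancy, yet they have the less explicit and shorter commitment. The drafters gave men both a start and a stop counted from the last dose. For women the stop has to be worked out from the definition of study end, and even then it attaches only to the bullet on trying to become pregnant. Neither the protocol nor the SAP says why the two differ.

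Both compounds are eliminated slowly, so the length of the post-dose period matters more than it would for a short-lived drug. A woman who follows the text exactly may stop contraception at about six weeks, while a pharmacologically active metabolite is still measurably present. The stake is avoidable exposure in early pregnancy. Nothing in the estimation or summary of any endpoint depends on it.

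**Working it through.** **Inputs.** Half-lives are 143 h (parent, Lu AF35700) and 250 h (metabolite, Lu AF36152), from Protocol 1.1.5.2. Follow-up is 42 (+3) days after last dose (8.5). The treatment period is 52 weeks and the follow-up period 6 weeks (3.1). The men's period is at least 3 months (5.3, criterion 10), taken here as about 90 days.

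**Plan's own figure.** 52 + 6 = 58 weeks, matching the Synopsis total for roll-over patients. 6 × 7 = 42 days, matching section 8.5. So the study extends 42 (+3) days beyond the last dose.

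**Simple decay.** Fraction left = 0.5^(24 × days / half-life in hours).

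- Day 42 is 1008 h: 1008/143 = 7.05 parent half-lives and 1008/250 = 4.03 metabolite half-lives.
- Day 45 is 1080 h: 7.55 and 4.32 half-lives.

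**Allowing for formation from parent (assumption).** Simple decay ignores metabolite still being made from remaining parent. Assume a first-order chain starting from steady state, with each half-life as that compound's own elimination half-life. The share of parent converted cancels, and the metabolite fraction left relative to steady state is

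(250 × Em − 143 × Ep) / (250 − 143),

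where Em and Ep are the simple-decay fractions for metabolite and parent. At day 42: (250 × 0.0611 − 143 × 0.0076) / 107 = 0.133.

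| Days after last dose | Parent left | Metabolite, simple decay | Metabolite, with formation |
|---|---|---|---|
| 42 | 0.76% | 6.1% | 13.3% |
| 45 | 0.53% | 5.0% | 11.0% |
| 52.1 | 0.23% | 3.1% | 7.0% |
| 90 | 0.003% | 0.25% | 0.58% |

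Day 52.1 is five metabolite half-lives (5 × 250 / 24).

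**Sensitivity to the half-lives.** Volume and clearance in section 1.1.5.2 give ln2 × 5442/29 = 130 h for parent and ln2 × 4933/15 = 228 h for metabolite, about 9% shorter than stated. A longer terminal half-life is expected from a two-compartment model, so this is not an error. With the shorter values, day 42 leaves 0.5^(1008/228) = 4.7% of metabolite by simple decay. The parent fraction is 0.5^(1008/130) = 0.46%, so the chain gives (228 × 0.0467 − 130 × 0.0046) / 98, about 10%. The picture is unchanged.

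**The case against.** The strongest case for the plan has five parts.

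1. **Women do have a period.** A reader might infer that roll-over women have no post-dose protection at all. The documents do not support that: the defined follow-up makes the study run six weeks past the last dose. This objection stands. What remains is that the contraception bullet has no end date, that the period is shorter than the men's without explanation, and that it is less certain for a patient who withdraws consent, whose follow-up is done only where feasible (8.5).
2. **Five half-lives is a convention.** A reader might infer that 42 days fails a standard. Neither document sets one. The parent clears five half-lives (29.8 days), and four metabolite half-lives (41.7 days) are just reached at day 42. This stands, so the point does not rest on that yardstick.
3. **The men's figure is a weak benchmark.** In the list for patients new to Lu AF35700, men are held to only 1 month or more. That shows the periods were not reconciled; it does not show that women's is long enough. SAP sections 2 and 5 say no such patients were enrolled, so the roll-over lists are the ones that count.
4. **No reproductive hazard is identified.** Section 1.1.4 reports negative genotoxicity, says fertility and developmental toxicity were studied, and regards no effect other than possible ECG changes as relevant to humans. This stands and lowers the severity.
5. **Safeguards exist.** Pregnant patients stop treatment (5.4), and pregnancies are reported on SAE timelines and followed (10.2). Section 10.5 adds: "SAEs that are spontaneously reported by a patient to the investigator after the safety follow-up assessment must be handled in the same manner" as those during the study. These act after conception, and the last has to be volunteered. Scheduled pregnancy tests end at the Primary Outcome/Withdrawal Visit (Panel 2).

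Consent pages are not in the reviewed copy and the Investigator's Brochure was not supplied. Either might state a period for women.

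**Conclusion.** The point holds at low severity. In both roll-over lists, women's commitment ends about 42 (+3) days after the last dose, reached only by way of the study-end definition. The contraception bullet is open-ended in wording, and men on the same drug are held to at least 3 months with no reason given. At day 42, under 1% of parent remains, with about 6% (simple decay) to 13% (formation from parent allowed for) of an active, less potent metabolite.

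These figures rest on preliminary population half-lives and first-order elimination; the upper one also rests on the steady-state chain. They compare lengths of cover. A reader might infer that women were put at demonstrated risk. The documents give no exposure threshold for reproductive harm and report no such hazard, so that inference is not supported. The missing end date and the unexplained difference between the sexes stand without any half-life argument.

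**What to change.** In criterion 9 of both roll-over lists, require women of childbearing potential to use highly effective contraception, and not to try to conceive, starting at the Baseline Visit and lasting at least 3 months beyond the final IMP dose, the same period as criterion 10. Align the consent wording; if consent already states a period for women, reconcile the two.

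A period of five metabolite half-lives (about 52 days) may look like a lighter compromise, but it leaves about 7% of metabolite under the chain model, against about 0.6% at day 90. Matching the men also removes the unexplained difference.

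The cost is one clause per list, the consent update, and up to about 90 − 42 = 48 more days of contraception for the women concerned. No visit, endpoint or analysis changes.
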